The Doppler ultrasound fetal gating device, which will be placed on the patient's abdomen by a registered MRI technician and held in place with a flexible elastic band, will be connected to the gating input of the MRI for either the entirety of, or a portion of the MRI examination. As is the case with all clinical ultrasound examinations, a water-based gel will be applied to the mother's skin below where the gating device is placed. Foam padding will be placed around the transducer cable to shield from possible heating of the cable. The gating device will detect when each fetal cardiac cycle begins and trigger MRI acquisition. MRI examinations will be up to 60 minutes in length. The MRI examination will be scheduled on the same day that volunteers have their clinical ultrasound appointment, with both examinations occurring within the shortest time-period that can reasonably be achieved.

Data Collection / Analysis

Anatomic MR images of the fetal heart (be they single or multi-slice), phase-contrast MR images of blood flow in great fetal vessels, and T1 and T2 maps in great fetal vessels will be acquired using prospective gating information from the Doppler ultrasound probe. Similarly, anatomical images, phase contrast images, and T1 and T2 maps will be acquired without any gating input. From the ultrasound examination during the patient's visit to the Fetal Echocardiography Clinic, we will retrieve anatomical images of the fetal heart in addition to flow waveforms acquired in the great fetal vessels.

MR data acquired without the Doppler ultrasound gating signal will be reconstructed without any gating information, and will also be reconstructed using retrospective gating techniques that we have previously developed [9], [10]. Anatomic MR images will be compared quantitatively in terms of myocardial border sharpness, with the anticipated result that Doppler gated MR will show higher border sharpness than un-gated or retrospectively gated MR. Ejection fraction will be calculated from anatomical cardiac images. These estimates of ejection fraction will be compared to ejection fraction calculated from the ultrasound images, with the anticipated result that Doppler gated MR will agree better with ultrasound images than un-gated or retrospectively gated MR.

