T1 and T2 maps will be compared in terms of the standard deviation of T1/T2 values in ROIs placed in the larger great fetal vessels, with the anticipated result that Doppler gated MR will provide a tighter distribution than un-gated or retrospectively gated MR. From the ungated, retrospectively gated, and Doppler ultrasound gated cardiac images, we will calculate *ejection fraction*.

Flow waveforms in great fetal vessels derived from retrospectively gated and Doppler ultrasound gated phase contrast images will be compared to flow waveforms measured with clinical Doppler ultrasound during the patient's visit to the Fetal Echocardiography Clinic (which we view as a gold standard). We anticipate that flow waveforms derived from Doppler ultrasound gated MR will prove to be more similar to the gold standard than flow waveforms derived from retrospectively gated MR.

Once enrolled, participants will be assigned a study number and all data and images gathered from the study procedures will be de-identified so to be identifiable only by this number and not any personal health information. Results of this study will be published in conference presentations and proceedings, peer reviewed journals, and academic rounds.

Inclusion and exclusion criteria

Inclusion criteria:

- pregnant adults (age 18 and up) with fetus affected by congenital heart disease
- singleton pregnancy in their 2nd and 3rd trimesters
- scheduled for a clinical fetal ultrasound examination at the Fetal Echocardiography Clinic at SickKids

Exclusion criteria:

Exclusion criteria that prevent the mother from having an MRI

- claustrophobia
- cardiac pacemaker
- non-MRI compatible implants

Other exclusion criteria

- non-singleton pregnancy
- obesity (BMI > 30)

Possible harm to the patients:

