Fetal MRI has been used for more than 25 years and poses no risk to the fetus in the 2nd and 3rd trimesters of pregnancy [11]. MRI does not use ionizing radiation, which is known to be harmful to the fetus, and risks are primarily related to the rise in body temperature due to absorption of radio-frequency energy. The UK National Radiological Protection Board suggests that MRI be restricted to the 2nd and 3rd trimester because of theoretical concerns about teratogenesis with MRI in early pregnancy [12], however recent studies of incidental MRI use in 1st trimester pregnancies have demonstrated no increase in adverse outcomes in these cases when no MR contrast agent is used [13]. In fetal MRI, current data and research studies have failed to demonstrate any reproducible harmful effects on pregnant women and their fetuses at magnetic field strengths of 3T or less [14]. The *International Commission on Non-Ionizing Radiation Protection* concludes that "adverse developmental effects [on the fetus] will be avoided with a margin of safety if the body temperature of pregnant women does not rise by more than 0.5 °C and the temperature of the fetus is less than 38 °C" [15].

MRI manufacturers have adapted the *International Electrotechnical Commission* (IEC) standard IEC 606-1-2-33, which defines three levels of MRI RF exposure risk. The lowest risk level, *normal mode*, sets a maximum specific absorption rate (SAR) of 2 W/kg and a maximum temperature rise of 0.5 °C. Before any MR pulse sequence is run, an estimate of whole-body SAR and temperature rise is made, which accounts for the patient's height, weight, ambient temperature and humidity, and details of the MR pulse sequence. When operating in normal mode, the scanner will simply not run a pulse sequence if the estimated SAR or temperature rise exceeds the thresholds defined by IEC normal mode. It is known that the fetal temperature rests ~0.5 °C above the maternal body temperature (which is 37 °C) due to limited pathways for heat transfer [16]. Numerical simulations suggest that fetal temperature will not pass 38°C when a mother is scanned in *normal mode* [16], giving assurance that we will operate within internationally recognized safety limits.

Concerns related to the loud noises generated by the MR coils and their potential to cause acoustic damage to the fetus have been dispelled by several studies [11].

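### The assurance that the fetus stays below 38 °C presumes a mother at 37 °C, but the protocol describes no check of her temperature

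*Protocol*

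**What the plan says.** The Possible harm to the patients section of the protocol quotes an international condition with two parts. The mother's body temperature may rise by no more than 0.5 °C, and "the temperature of the fetus is less than 38 °C". The first part limits a change; the second is an absolute temperature.

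The control it describes is the scanner's normal mode, which "sets a maximum specific absorption rate (SAR) of 2 W/kg and a maximum temperature rise of 0.5 °C". Before each sequence the scanner estimates SAR and temperature rise in a calculation "which accounts for the patient's height, weight, ambient temperature and humidity, and details of the MR pulse sequence". The mother's own temperature is not among those inputs.

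For the absolute part, the section states that "fetal temperature rests ~0.5 °C above the maternal body temperature (which is 37 °C". It then says: "Numerical simulations suggest that fetal temperature will not pass 38°C when a mother is scanned in" normal mode. From this it concludes: "giving assurance that we will operate within internationally recognized safety limits".

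Elsewhere, Procedures says that "MRI examinations will be up to 60 minutes in length" and describes placing the gating device, but no temperature reading. Inclusion and exclusion criteria has a list headed "Exclusion criteria that prevent the mother from having an MRI" (claustrophobia, pacemaker, incompatible implants) and a second list (non-singleton pregnancy, BMI above 30). Neither mentions fever or temperature.

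**The concern.** The control and the claim do not match. A cap on temperature rise says nothing about where the mother starts, so it cannot detect a raised baseline. The absolute fetal condition therefore depends on her starting temperature, which the protocol takes as 37 °C and does not plan to verify.

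At stake is a research scan, which can be postponed, going ahead in a mother for whom the protocol's own safety condition already fails. The protocol names heating as the main risk of MRI and, under Possible benefit to the patient, calls the chance of benefit very small. That leaves little reason to scan outside the adopted condition when a temperature reading would show the problem beforehand.

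**Working it through.** **Inputs, all from Possible harm to the patients:** fetal condition below 38 °C (strict); resting fetal offset about +0.5 °C; maternal temperature 37 °C; normal-mode cap on temperature rise 0.5 °C.

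**Step 1: the protocol's own figure.** At rest, fetus = mother + offset = 37.0 + 0.5 = 37.5 °C. Adding the full permitted rise, on the assumption that the fetus warms as much as the mother, gives 37.5 + 0.5 = 38.0 °C. This agrees with the statement that simulations suggest 38 °C will not be passed. It is only a consistency check: the protocol attributes its statement to cited simulations, whose conditions cannot be seen here.

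**Step 2: resting fetal temperature at other maternal temperatures,** assuming the offset still holds above 37 °C.

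| Mother (°C) | Fetus before scanning (°C) | Room below 38 °C |
|---|---|---|
| 37.0 | 37.5 | 0.5 |
| 37.2 | 37.7 | 0.3 |
| 37.4 | 37.9 | 0.1 |
| 37.5 | 38.0 | 0.0 (condition not met) |
| 37.8 | 38.3 | −0.3 (condition not met) |

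**Step 3: the maternal temperature at which the condition fails before scanning** is 38 − offset = 38 − 0.5 = 37.5 °C. The offset is stated only approximately. Assumed values of 0.4 and 0.6 °C give 37.6 and 37.4 °C; a wider assumed range of 0.3 to 0.7 °C gives 37.7 to 37.3 °C.

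**Step 4: can any described safeguard detect this?** The scanner check uses estimated SAR and estimated rise, and neither depends on the mother's measured temperature as the protocol describes them. Procedures has no reading, and the exclusion lists have no temperature criterion. Following the text as written, a mother at 37.5 °C would be scanned.

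**The case against.** The strongest reply is that this is an omission, not a misstatement. The protocol gives an ordinary maternal temperature and hedges the simulation result. Day-of-scan checks often sit in a hospital's MRI procedures; the Rationale section commits the study to GCP and the hospital's requirements, and a registered MRI technician places the device. The exclusion lists deal with enrolment and lasting contraindications, so the absence of a transient temperature there is weak evidence of what would happen on the day. All of this stands as far as it goes: screening may well exist. But the protocol does not state it, and it draws an assurance about the whole study from a premise that it does not describe checking.

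The reply also notes that the 37.5 °C figure carries an approximate resting offset beyond the temperature for which it was stated. That is true, and it is why the figure is given as approximate and conditional.

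Three stronger readings are tempting and should not be drawn:

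- **That a mother at 37.0 to 37.5 °C would breach the limit during the scan.** The addition in step 1 reaches 38.0 °C from 37.0 °C, but only if the fetus warms by the full permitted amount. The protocol does not give fetal warming, so no claim is made for that band.
- **That fetuses would be harmed.** The quoted condition says that effects are avoided with a margin of safety if both parts hold. It is not a threshold of harm. A fetus at 38 °C before the scan is there because of the mother's temperature, not the study, and the scanner caps the added heating.
- **That febrile mothers would in practice be scanned.** The document shows only that no check is written down.

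**Conclusion.** The point holds in a limited form. The assurance covers an absolute fetal temperature, while the described control limits only SAR and rise, and the maternal temperature that links the two is presumed. At about 37.5 °C or more (37.4 to 37.6 °C for assumed offsets of 0.6 to 0.4 °C), the fetal condition is not met even before scanning.

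This rests on the protocol's approximate offset continuing to apply above 37 °C, and on there being no unstated hospital screening. Severity is low: the condition includes a safety margin, added heating is capped, and the documents give no basis for estimating how many of the 20 volunteers would be affected. It is still worth correcting, because the remedy is small and the scan can be deferred.

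**What to change.** 1. **Procedures:** record maternal temperature on the day, before the participant enters the scanner, and name the method. Defer the scan at or above a cut-off of at most 37.5 °C. The safety reviewers should set it lower if room is to be kept for warming during the scan, because at 37.4 °C only about 0.1 °C remains. This is a day-of-scan check, not an enrolment criterion.
2. **If hospital MRI screening already does this,** cite it and its cut-off instead.
3. **Possible harm to the patients:** state that the assurance rests on simulations and on a maternal temperature of about 37 °C. Do not extend it to every mother below 37.5 °C; passing the check does not show that the fetus stays below 38 °C throughout the scan.
4. **Deferred scans:** rebook with a later clinical ultrasound where possible. Otherwise mark that participant's ejection fraction and flow waveform comparisons with ultrasound as not same-day. The MRI-only comparisons (border sharpness, spread of T1 and T2) are unaffected by the lost pairing.

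**Cost:** 20 temperature readings and a few lines of text. The downside is an occasional deferral, of unknown frequency. Each one that cannot be rebooked with an ultrasound loses the same-day comparison for 1 of 20 participants (5%), or 1 of 10 in a trimester group (10%). Rebooking would cost $33.50 if only travel is paid again, or up to 500 + 33.50 = $533.50 if the unused slot is charged; both billing outcomes are assumptions. The planned total is 20 × 500 + 20 × 33.50 + 2,000 = $12,670, which leaves 30,000 − 12,670 = $17,330 of the available funding.

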In addition to the ultrasound that volunteers will undergo to validate our MRI techniques, ultrasound is the enabling technology behind the Doppler ultrasound probe used for fetal cardiac gating. Doppler ultrasound detects blood velocity by transmitting acoustic waves into the patient and then detecting waves that reflect back from moving red blood cells. Ultrasounds are included in routine prenatal care around the world and no harmful effects have ever been detected. Theoretical concerns are related to tissue heating (as in MRI) in addition to ultrasonic gaseous cavitation [17]. The Doppler ultrasound probe will be built by our collaborators from the Department of Diagnostic and Interventional Radiology at the University Medical Centre in Hamburg, Germany where they have received ethics approval for use in non-pregnant adult human volunteers [6] and later, for fetal imaging in pregnant adult volunteers [7]. The transducer transmits acoustic energy at a maximum (pulse averaged) power of 1.5 mW/cm², which is well below the limit of 20 mW/cm² set by Health Canada for Doppler ultrasound based fetal heart rate monitors [18].

This study will not proceed before we receive Health Canada approval to use this new medical device.

It is known that use of ultrasonic gels carries a small risk of spreading bacterial infections [19]. Health Canada mandates that sterile gels be used in all procedures that pass a device through tissue (such as ultrasound guided tissue biopsy) or where the ultrasound transducer makes contact with a mucus membrane. Because we will only put the ultrasound gel on intact skin, there is minimal risk of spreading infection. The ultrasound transducer will be cleaned with an antibacterial disinfectant after each use, and Health Canada guide-lines regarding use of non-sterile ultrasound gels, as outlined in [20] will be followed.

The device manufacturer reports that in rare circumstances, the cable that connects to the transducer can heat to up to 70 °C. They have insulated the cable with foam padding. With the insulation attached, the surface temperature of the cable will not exceed 43 °C. Since the cable can make contact with the participant's skin, this may cause minor discomfort.

Any adverse events (such as injury during MRI examination) will be reported to the SickKids Research Ethics Board.

Possible benefit to the patient:

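### Do the protocol's own temperature figures undercut its assurance that scanning stays within the fetal safety limit?

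*Protocol*

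**What the plan says.** All the figures are in the Protocol, section on possible harm to the patients.

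- **The criterion.** The protocol quotes an international body: developmental harm is avoided, with a safety margin, provided maternal body temperature "does not rise by more than 0.5 °C and the temperature of the fetus is less than 38 °C".
- **The scanner's cap.** The lowest exposure level, normal mode, "sets a maximum specific absorption rate (SAR) of 2 W/kg and a maximum temperature rise of 0.5 °C". The scanner refuses a sequence whose estimate is above either threshold. The estimate takes in the patient's height and "weight, ambient temperature and humidity, and details of the MR pulse sequence".
- **The baseline.** "It is known that the fetal temperature rests ~0.5 °C above the maternal body temperature (which is 37 °C").
- **The evidence for the fetal limit.** Cited numerical simulations suggest that the fetus does not go above 38 °C in normal mode, "giving assurance that we will operate within internationally recognized safety limits".
- **The cable.** Later in the same section the manufacturer is said to report that "in rare circumstances, the cable that connects to the transducer can heat to up to 70 °C". With foam insulation the surface stays at or below 43 °C, and the stated consequence is minor discomfort on the skin. The study may not start without Health Canada approval of the device.

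The Procedures section names the two 3T scanners, the placement of the probe and an examination of up to 60 minutes. It does not repeat that scans run in normal mode.

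**The concern.** The criterion requires that "the temperature of the fetus is less than 38 °C", a strict inequality. The simulations are reported as showing only that 38 °C is not exceeded, which is weaker. Adding the protocol's own resting temperatures to the permitted rise lands exactly on 38.0 °C. A reader could fairly conclude that the assurance has no room in it, and that a mother slightly warmer than 37 °C would push the fetus past the limit.

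Three further points seem to weaken the assurance. The probe and cable are not among the listed inputs to the scanner's estimate, although the cable can heat. The argument depends on a scan mode that the Procedures do not name. The section also opens by saying that fetal MRI carries no fetal risk in the second and third trimesters, and its next sentence describes a thermal risk.

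At stake is whether the ethics board was given a fetal safety statement that does not follow from the numbers beside it.

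**Working it through.** **Inputs**, all from the section on possible harm:

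- maternal temperature M = 37 °C
- fetal offset d ≈ 0.5 °C
- maximum rise in normal mode R = 0.5 °C
- fetal criterion: below 38 °C
- simulation result: at most 38 °C

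One input is not in the protocol: the ratio k of fetal to maternal warming. The sum behind the concern takes k = 1.

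**Formula.** Fetal temperature at the cap = M + d + k × R.

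**The protocol's own figure.** With k = 1: 37 + 0.5 + 1 × 0.5 = 38.0 °C. This agrees with the simulation statement (at most 38 °C), so the protocol contains no arithmetic error. It does not meet a strict reading of the criterion: 38 − 38.0 = 0.0 °C of margin.

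**How firm is 38.0?** Change one input at a time:

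| Change (assumed) | Sum | Result |
|---|---|---|
| k = 0.8 | 37.5 + 0.8 × 0.5 | 37.9 °C |
| k = 1.2 | 37.5 + 1.2 × 0.5 | 38.1 °C |
| d = 0.4 | 37 + 0.4 + 0.5 | 37.9 °C |
| d = 0.6 | 37 + 0.6 + 0.5 | 38.1 °C |
| M = 36.8 | 36.8 + 0.5 + 0.5 | 37.8 °C |
| M = 37.2 | 37.2 + 0.5 + 0.5 | 38.2 °C |
| R reached = 0.4 (below the cap) | 37.5 + 0.4 | 37.9 °C |

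The result falls on either side of 38 with shifts of 0.1 to 0.2 °C in inputs that the protocol gives only roughly or not at all. The offset is marked as approximate. If that meant 0.45 to 0.55 °C, the result would run from 37.95 to 38.05 °C. The figures cannot separate a value at 38 from one just below it.

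**The two parts of the criterion.** The maternal part applies "if the body temperature of pregnant women does not rise by more than 0.5 °C", and the normal-mode cap is the same 0.5 °C, so that part is met. Only the fetal part is in question. For it the protocol relies on the simulations, whose peak temperature, model and baseline it does not report.

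**The cable.** A contribution to fetal temperature would need a figure for heat passing from an insulated surface of at most 43 °C, through the skin, to the maternal core or fetus. The protocol gives none, so nothing can be computed in either direction.

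**The case for a change.** The strongest case for a change needs no heat-transfer assumption. A result of at most 38 °C does not establish a temperature below 38 °C, yet the assurance is drawn directly from it. The scanner does not close the gap: it estimates whole-body absorption and temperature rise, not fetal temperature, and it blocks a sequence only above the cap, so one estimated at exactly 0.5 °C would run. The mode is not written into the Procedures. The text does not say whether the estimate or the simulations included a probe and cable on the abdomen.

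Some of this stands. The two phrases differ in strength, the protocol demonstrates no margin at the cap, and the coverage of the device is undocumented.

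The rest does not carry. The difference matters only for a scan exactly at the boundary, and the protocol's approximate figures cannot resolve that boundary. The warmer maternal temperatures are not the protocol's; it gives 37 °C. The protocol claims to work within recognized limits and claims no margin of its own; the safety margin belongs to the quoted criterion. The sentence of assurance ties the study's own operation to normal mode, so the intended mode is plain even though the Procedures do not repeat it. The cable is disclosed and treated separately as a matter of skin contact, with insulation, and the device needs regulatory approval before the study starts. The sweeping opening statement about risk is qualified by the sentence that follows it.

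**Conclusion.** The concern does not call for a change to the plan. It correctly notes that the cited limit is strict and the supporting statement is not, and that the protocol's rounded figures put the fetus at about 38.0 °C at the cap, with a margin of 0.0 °C. That value assumes a maternal temperature of 37 °C, an offset of exactly 0.5 °C, one-for-one fetal warming and a scan at the full permitted rise. It agrees with the simulation result on which the protocol relies, and no breach is shown. The documents do not support the claim that the cable undermines the fetal limit.

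The remaining points are loose wording (two phrases of unequal strength and an over-broad opening statement) and missing detail: the scan mode, which the assurance already implies, and whether the simulations covered the device. Rewording would make the section tidier, but it would alter no scan, exposure limit, measurement, comparison or conclusion. This judgement does not vouch for the simulations, which cannot be examined here, and takes no view on what the clinical limits should be.
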